
pre-clinical data support the evaluation of neoantigen vaccines as an effective cancer treatment. Although studied extensively in pre-clinical models, only one limited human trial has been published. In this trial, a group from Washington University in St. Louis reported on a first-in-man clinical trial evaluating neoantigen vaccine in patients with metastatic melanoma⁶. The researchers vaccinated three patients with mature dendritic cells presenting seven predicted mutation-specific HLA-A*02:01 restricted epitopes. They showed that vaccination with high affinity, patient specific mutated epitopes augmented T cell immunity directed against naturally occurring dominant neoantigens and broadened the response by revealing subdominant neoantigens; but no clinical responses were observed. However, this did show that vaccination against mutated epitopes was safe as none of the three patients experienced any autoimmune adverse events.

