As shown by the NCI SB, neoantigen specific cells can be found both in the tumor and in the blood of cancer patients^{7,10}. To boost responses against defined neoantigens, we are using a systemic vaccine dose and schedule covering both the blood and peripheral tissues. For that purpose, we decided to use two routes of administration: Intravenous (IV) to stimulate T cells that reside in the lungs, spleen and the bone marrow of the patients and subcutaneously (SQ) to stimulate T cells residing in peripheral lymph nodes. This concept was also shown before in a mouse model¹⁶. Recently, a group from Washington University in St. Louis (WUSTL) reported on a first-in-man clinical trial evaluating neoantigen vaccine in patients with metastatic melanoma⁶. The researchers vaccinated three patients IV with mature dendritic cells presenting seven predicted mutation-specific HLA-A*02:01 restricted epitopes. They showed that vaccination with patient specific mutated epitopes augmented T cell immunity directed against naturally occurring dominant neoantigens and broadened the response by revealing subdominant neoantigens. The initial priming dose they used was 1.5×10^7 DC per peptide (9 peptides in total, 1.35×10^8 DC total), and all the subsequent doses were 5.0×10^6 DC per peptide (4.5×10^7 DC total). In our trial, we plan to load DC with a peptide pool containing all defined epitopes recognized by TIL. Therefore, we chose a dose level similar to the doses used during the WUSTL trial for the IV administration. In a different phase I/II clinical trial of sequential SQ and IV delivery of a dendritic cell vaccine for refractory multiple myeloma¹⁷, patients were vaccinated with increasing doses of $5 \times$ -, $10 \times$ -, 50×10^6 cells and $10 \times$ -, 50×10^6 cells respectively. The treatment was well tolerated, and no severe adverse events occurred. Therefore, we decided to vaccinate with DC doses which are not higher than 50×10^6 for the SQ and the IV route of administration. We are planning to give the maximal dose possible according to our manufacturing yields to allow efficient activation of circulating and tissue resident neoantigen specific cells.

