3.1.2 Treatment Phase

The protocol will consist of two cohorts: cohort 1, patients with melanoma and cohort 2, patients with epithelial cancer.

The study will utilize an optimal design where initially 21 evaluable patients will be enrolled to each cohort. If 0 or 1 of the 21 patients in a given cohort experiences a clinical response, then no further patients will be enrolled; if 2 or more of the first 21 evaluable patients enrolled have a clinical response, then accrual will continue until a total of 41 evaluable patients have been enrolled to that cohort.

Patients will receive no other experimental agents while on this protocol. All patients will receive one course of treatment (4 vaccination cycles). The start date of the course will be the start date of the first vaccination; the end date will be the day of the first post-treatment evaluation (week 8 if the patient receives all 4 cycles).

Enrollment will be staggered within each cohort with three weeks between start dates for the first three patients to allow for a 3-week interval for safety assessment before the next enrolled patient is scheduled to receive their first dose of the DC vaccine.

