3.1.3 Protocol Stopping Rules

New subject enrollment to the protocol will be temporarily halted if any of the following conditions are met, and discussions will be had with the FDA or NIH IRB regarding protocol revisions if applicable:

- If one or more treatment-related death occurs due to vaccination, we will promptly discuss this with the NCI IRB and the FDA.
- Two or more patients develop a grade 3 or greater toxicity at any point in the study not attributable to disease progression (or circumstances unrelated to the study).
 - The following grade 3 reactions commonly associated with immunization **will not** be included in this protocol stopping rule:
 - Pruritus/itching: intense or widespread and interfering with ADL lasting <72 hours
 - Fatigue: severe fatigue interfering with ADL lasting < 72 hours
 - Fever: > 40.0°C for < 24 hours
 - Local lymphadenopathy lasting < 1 week
- If one of the first three patients (or 2 of the first 6 patients, or 3 of the first 9 patients, or 4 of the first 12 patients) develop grade 3 autoimmunity, that cannot be resolved to less than or equal to a grade 2 autoimmune toxicity within 10 days, or any grade 4 or greater autoimmune toxicity.

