3.6.1 Criteria for Removal from Protocol Therapy

Patients will be taken off treatment for the following:

- Completion of treatment
- Grade 3 or 4 toxicity due to the vaccine, excluding those known events such as local injection site reactions, skin rash, pruritus, fatigue, fever and local adenopathy.
- Progression of disease
- Participant requests to be withdrawn from active therapy
- Investigator discretion
- Positive pregnancy test

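### Read as written, the autoimmunity stopping rule in 3.1.3 would not automatically pause enrollment after a single non-fatal grade 4 autoimmune event beyond the first three patients

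*Combined protocol and SAP*

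**What the plan says.** Section 3.1.3 lists three conditions, any one of which temporarily halts new enrollment.

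- Condition 1: one or more treatment-related deaths.
- Condition 2: "Two or more patients develop a grade 3 or greater toxicity at any point in the study", if "not attributable to disease progression (or circumstances unrelated to the study"). Some short-lived grade 3 immunization reactions (itching, fatigue, fever, local lymphadenopathy) are exempt. Autoimmunity is not.
- Condition 3: a single sentence. It opens with the counts, "If one of the first three patients (or 2 of the first 6 patients, or 3 of the first 9 patients", and adds four of the first twelve. It then names two kinds of event: grade 3 autoimmunity that does not come down to grade 2 or less, and the closing phrase, "autoimmune toxicity within 10 days, or any grade 4 or greater autoimmune toxicity". It carries no wording about attribution.

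Elsewhere, 3.6.1 takes a patient off treatment for "Grade 3 or 4 toxicity due to the vaccine, excluding those known events". Sections 7.2.1, 7.3 and 7.5.1 set the reporting duties. Section 11.2 names autoimmune reactions as a possible risk, because the peptides may resemble natural proteins.

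**The concern.** The closing phrase of condition 3 can be read in two ways, and they require different actions for the same event. By grammar, it is a second object of the one verb in the sentence, so the subject with its counts applies: a grade 4 event matters only if it occurs in one of the first three patients, two of the first six, and so on, with no count defined after patient 12. By the word 'any' and the comma before it, one grade 4 event is enough at any time.

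The grammatical reading gives the less cautious action for the more severe event. A stopping rule is meant to settle such a decision in advance. Here the team would have to interpret the rule after a life-threatening event of the kind the protocol itself identifies as a risk.

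**Working it through.** The plan states no operating characteristics for its safety rule, so there is no figure to reproduce.

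**Step 1: apply the three conditions to one event.** Take one non-fatal grade 4 autoimmune event in patient k, with no counted grade 3 or higher toxicity in any other patient.

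| Condition in 3.1.3 | Needs | k = 1 to 3 | k = 4 or later |
|---|---|---|---|
| 1 | a treatment-related death | not met | not met |
| 2 | two patients | not met | not met |
| 3, counts govern grade 4 | 1/3, 2/6, 3/9 or 4/12 | met | not met |
| 3, 'any' stands alone | one patient | met | met |

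The two readings part from patient 4 onward. Among all sets of one to four events in the first twelve patients, the only sets that meet condition 3 by its counts without also meeting condition 2 are a single event in patient 1, 2 or 3. For events that condition 2 counts, the later tiers therefore add nothing. They can matter only for events that condition 2 leaves out as due to progression or unrelated to the study.

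**Step 2: look for another rule that pauses enrollment.** Section 3.6.1 stops treatment for the affected patient. Section 7.3 sends serious events to the sponsor, 7.2.1 sends unanticipated problems to the IRB and Clinical Director within 7 days, and 7.5.1 sends safety concerns to the IRB at once. None of these pauses enrollment by itself.

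**Step 3: size, under assumed rates only.** Let r be the per-patient chance of non-fatal grade 4 autoimmunity, q the chance of other counted grade 3 or higher toxicity, t = r + q, and n the number enrolled. The first three patients are counted across the protocol, and patient order is taken as event order. The assumed values are r = 0.1% to 2% and q = 2%, 5% and 10%. From 8.2, n = 42 if both cohorts stop after stage 1 (2 × 21), and n = 86 at most.

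- Chance that the readings diverge: (r/t) × [(1−t)^3 − (1−t)^n].
- Chance that the literal rule never halts although the other reading would: (n−3) × r × (1−t)^(n−1).

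Example, r = 0.5%, q = 2%, n = 42:

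- Diverge: 0.2 × (0.9269 − 0.3453) = 0.116.
- Never halts: 39 × 0.005 × 0.975^41 = 0.195 × 0.354 = 0.069.

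| n | q | Diverge, r = 0.1% / 0.5% / 1% / 2% | Never halts, same r |
|---|---|---|---|
| 42 | 2% | 2.5 / 11.6 / 21.2 / 35.2% | 1.6 / 6.9 / 11.2 / 14.6% |
| 42 | 5% | 1.5 / 6.8 / 12.6 / 21.6% | 0.5 / 1.9 / 3.1 / 4.0% |
| 42 | 10% | 0.7 / 3.4 / 6.3 / 11.3% | 0.1 / 0.2 / 0.3 / 0.4% |
| 86 | 2% | 3.7 / 16.3 / 28.0 / 42.7% | 1.4 / 4.8 / 6.2 / 5.2% |
| 86 | 5% | 1.7 / 7.6 / 13.8 / 22.9% | 0.1 / 0.3 / 0.4 / 0.4% |
| 86 | 10% | 0.7 / 3.4 / 6.4 / 11.4% | all under 0.1% |

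The gap between the two columns is delay, not absence of a halt. After divergence, the mean number of further patients who start before condition 2 is met or accrual ends is about 8 to 17 for n = 42, and about 8 to 30 for n = 86.

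The 86-patient case is a ceiling. A cohort passes stage 1 (two or more responses in 21) with probability 0.283 at a 5% response rate and 0.942 at 20%, so both pass with probability 0.283² = 0.08 and 0.942² = 0.89.

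**The case against.** The strongest reply is that a clinician would read 'any' in its ordinary sense, pause after one grade 4 event, and no defect would arise. That is plausible. 'Any' does little work under the counted reading, and having no autoimmune trigger after patient 12 would be odd. But this shows only that the sentence can be read safely. It does not remove the other reading, which is the grammatical one.

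A second reply is that the consequence is small, since the sponsor and the IRB would be informed and could pause at discretion. This stands, and it limits the point to automatic versus discretionary.

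A third is that the magnitudes do not measure this trial. This also stands. The human experience cited is small and reassuring: in the three-patient melanoma study (1.2.1), "none of the three patients experienced any autoimmune adverse events"; for the myeloma trial (1.2.5), "The treatment was well tolerated, and no severe adverse events occurred". At q = 10% the never-halting chance is about 0.4% or less. The calculations also assume that the literal reading is always applied and discretion never used.

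A reader might infer more: that the trial would carry on unchecked after a life-threatening autoimmune event, or that the overlap with condition 2 proves the sponsor meant a single-event trigger. The documents support neither. The reporting and patient-level safeguards apply under both readings, and the grade 3 tiers overlap condition 2 in the same way, so the overlap says nothing about intent.

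**Conclusion.** The point holds as a wording fault in a safety rule. Applied literally, 3.1.3 does not require a pause after one non-fatal grade 4 autoimmune event beyond the first three patients when no other patient has a counted grade 3 or higher toxicity. All three qualifiers are needed: a related death meets condition 1, a second counted patient meets condition 2, and an event in the first three patients meets condition 3.

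What is affected is whether a temporary pause is automatic or discretionary in the interval before a second counted patient. How often that would arise cannot be stated. The percentages above are illustrations across assumed rates and should not be quoted as this trial's risk. The response-rate design is untouched.

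One related matter needs only clarification. Section 3.1.3 does not say whether the first three patients are counted across the protocol or per cohort. Its title, and its halt of the whole protocol, lean toward the former. Section 3.1.2 specifies the cohort where it means it: "Enrollment will be staggered within each cohort with three weeks between start dates for the first three patients". The wording problem arises under either count.

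**What to change.** Take the grade 4 phrase out of condition 3 and make it a separate bullet, for example: *One patient, at any time during the study, has an autoimmune toxicity of grade 4 or higher.* Keep the 1/3, 2/6, 3/9 and 4/12 counts for unresolved grade 3 autoimmunity only, and state whether they run per cohort or across the protocol.

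Do not carry over the attribution wording of condition 2. Condition 3 has no such filter now, so adding one would drop grade 4 autoimmune events judged unrelated, including those in the first three patients that halt enrollment today.

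If the sponsor did intend the counts to govern grade 4 events, this changes the rule rather than clarifying it; the sponsor should then say so and give the reason.

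The cost is a one-line amendment and possibly one extra temporary enrollment pause, including for an event later judged unrelated.

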3.2 DRUG ADMINISTRATION

Patients will receive peptide pulsed dendritic cell vaccines on days 0, 14 (\pm 5 days), 28 (\pm 5 days), and 42 (\pm 5 days). The vaccine will be administered as both an intravenous (IV) infusion

and a subcutaneous (SQ) injection. The total dose will be divided equally between IV and SQ containing 1.0×10^7 to 8.0×10^7 cells per cycle depending upon the manufacturing yield.

The patient's dendritic cell products will be delivered to the Patient Care Unit by a staff member from the NCI SB. Prior to infusion, the cell product identity labels on the syringe and cell infusion bag will be double-checked by two authorized staff (MD or RN), an identification of the product and documentation of administration are entered in the patient's chart, as is done for blood banking protocols.

- Cells for SQ injection will be administered first, followed by cells for IV infusion.
- Cells for SQ injection will be administered in a total of 1.0 mL (0.5×10^7 to 4.0×10^7 cells) into the deep subcutaneous tissue of a proximal extremity. Injections will preferentially be administered in the anterior thigh. Injections will not be given into extremities that have had radical lymph node dissections. The same extremity will be used for each cycle of the peptide loaded dendritic cell vaccine administration.
- Cells for IV administration (0.5×10^7 to 4.0×10^7 cells) will be infused over 20 to 30 minutes, or as clinically determined by an investigator for patient safety, via non-filtered tubing, gently agitating the bag during infusion to prevent cell clumping. See **Appendix 1** for cell infusion instructions.
- Vital signs will be monitored hourly (± 15 minutes) for two hours. The post-administration monitoring period may be adjusted by the PI.
- All patients will receive their peptide pulsed dendritic cell vaccines in the NIH Clinical Center. The first three patients will receive their Day 0 SQ injection and IV infusion on the In-Patient Care Unit, and then will receive their subsequent SQ injections and IV infusions (days 14, 28, and 42) as outpatient procedures in the 3SE-S Day Hospital. All patients enrolled after the first three patients will receive their full course of SQ injections and IV infusions (days 0, 14, 28, and 42) as outpatient procedures in the 3SE-S Day Hospital. This schedule may be adjusted by the PI as clinically appropriate.

3.3 ON-STUDY EVALUATION

3.3.1 Within 7 Days Prior to the 1st Vaccination (Day 0)

- Repeat all screening procedures from Section **2.2.3** if not completed within 7 days prior to the 1st vaccination (Day 0).

3.3.2 Within 2 Days Prior to the 1st Vaccination (Day 0)

- Lymphocyte phenotyping (TBNK)
- Review of baseline symptoms
- Research samples as described in Section **5**

3.3.3 Within 2 Days Prior to Each Subsequent Vaccination (Days 14, 28, and 42 (± 5 days))

- Physical examination, including ECOG
- Vital signs
- CBC w/differential

- Acute Care Panel (sodium, potassium, chloride, bicarbonate, creatinine, glucose, BUN), Hepatic Panel (alkaline phosphatase, AST, ALT, total bilirubin, direct bilirubin), Mineral Panel (albumin, calcium, magnesium, phosphorus), Uric Acid, Creatinine Kinase, Lactate Dehydrogenase, Total Protein
- β -HCG pregnancy test (serum or urine) on all females of child-bearing potential
- Toxicity assessment, including a review of systems
- Research samples as described in Section **5**

3.3.4 After Each Vaccination

- Vital signs will be monitored hourly (\pm 15 minutes) for two hours. The post-administration monitoring period may be adjusted by the PI.

3.4 POST-TREATMENT EVALUATION (FOLLOW-UP)

3.4.1 1st Follow-up Evaluation (Day 56 \pm 5 days)

All patients will return to the NIH Clinical Center for their first follow-up evaluation on day 56 (\pm 5 days), which is approximately 2 weeks from the 4th vaccination.

At the first follow-up evaluation, patients will undergo:

- Physical examination, including ECOG
- Vital signs
- CBC w/differential
- Acute Care Panel (sodium, potassium, chloride, bicarbonate, creatinine, glucose, BUN), Hepatic Panel (alkaline phosphatase, AST, ALT, total bilirubin, direct bilirubin), Mineral Panel (albumin, calcium, magnesium, phosphorus), Uric Acid, Creatinine Kinase, Lactate Dehydrogenase, Total Protein
- Lymphocyte phenotyping (TBNK)
- β -HCG pregnancy test (serum or urine) on all females of child-bearing potential
- Toxicity assessment, including a review of systems
- Research samples as described in Section **5**
- Imaging studies as performed at baseline to determine tumor response. If clinically indicated, other scans or x-rays may be performed, e.g., brain MRI, bone scan.
- A 5-liter leukapheresis may be performed. If the patient is unable to undergo leukapheresis, approximately 96 mL of blood may be obtained. This will be conducted under 03-C-0277.

3.4.2 Subsequent Follow-up Evaluations

The second follow-up evaluation will take place 1 month (\pm 5 days) after the first follow-up evaluation (Day 56). Subsequent follow-up evaluations will take place every 1-2 months for the first year, and then annually or as clinically appropriate as determined by the PI. As noted in Section **3.4.1**, additional leukapheresis may be performed only at the first follow-up evaluation. It will not be performed at any other post-treatment evaluations.

Note: Patients may be seen more frequently as clinically indicated.

At each scheduled follow-up evaluation, patients will undergo:

- Physical examination, including ECOG
- Vital signs
- CBC w/differential
- Acute Care Panel (sodium, potassium, chloride, bicarbonate, creatinine, glucose, BUN), Hepatic Panel (alkaline phosphatase, AST, ALT, total bilirubin, direct bilirubin), Mineral Panel (albumin, calcium, magnesium, phosphorus), Uric Acid, Creatinine Kinase, Lactate Dehydrogenase, Total Protein
- Lymphocyte phenotyping (TBNK)
- β -HCG pregnancy test (serum or urine) on all females of child-bearing potential (complete at all follow-up evaluations within 4 months after the last vaccine)
- Toxicity assessment, including a review of systems
- Research samples as described in Section **5**
- Imaging studies as performed at baseline to determine tumor response. If clinically indicated, other scans or x-rays may be performed, e.g., brain MRI, bone scan.

Note: Patients who are unable or unwilling to return for follow-up evaluations may be followed via phone or e-mail contact. Patients may be asked to send laboratory, imaging and physician exam reports performed by their treating physician.

3.5 STUDY CALENDAR

Assessments	Screening/Baseline (prior to enrollment on treatment protocol)			On-Study/Course of Treatment (1 vaccine = 1 cycle)			Post-Treatment Follow-up		
	Within 3 Months	Within 4 Weeks	Within 7 Days	Day 0 ¹	Day 14 (±5 d)	Day 28 (±5 d)	Day 42 (±5 d)	Day 56 (±5 d)	Subsequent Follow-up Visits ²
Informed consent ³									
Confirmation of diagnosis by NCI Lab of Pathology ⁴	X								
Medical history ⁵	X								
Physical exam	X			X	X	X	X	X	X
Performance score (ECOG) ⁶				X	X	X	X	X	X
Vital signs ⁷				X	X	X	X	X	X
β-HCG pregnancy test ⁸				X	X	X	X	X	X
Urinalysis ⁹				X	X	X	X	X	X
EKG				X	X				
Toxicity assessment					X	X	X	X	X
Laboratory Procedures									
Viral testing ¹⁰		X							

1 Assessments (except TBNK and research samples) may be done within 7 days prior to the first vaccination on Day 0. **Lymphocyte phenotyping (TBNK) and research samples must be drawn within 2 days prior to the first vaccination on Day 0.**

2 The second follow-up evaluation will take place 1 month (± 5 days) after the first follow-up evaluation (Day 56). Subsequent follow-up evaluations will take place every 1-2 months for the first year, and then annually or as clinically appropriate as determined by the PI. Patients may be seen more frequently as clinically indicated. Patients who are unable or unwilling to return for follow-up evaluations may be followed via phone or email contact. Patients may be asked to send laboratory, imaging and physician exam reports performed by their treating physician.

3 The date of enrollment is the date the subject signs the written informed consent document. The patient will be consented and enrolled on this protocol once the patient has adequate leukapheresis material banked by the SB CPF and prior to administration of the first vaccine.

4 Confirmation of diagnosis of metastatic melanoma or epithelial cancer. Testing is permitted to be conducted at any time prior to enrollment.

5 Patient history may be obtained within 8 weeks prior to enrollment.

6 ECOG of 0, 1, or 2.

7 After each vaccination, vital signs will be monitored hourly (± 15 minutes) for two hours. The post-administration monitoring period may be adjusted by the PI. Complete at all follow-up evaluations within 4 months after the last vaccine.

8 Serum or urine; on all females of child-bearing potential.

9 With culture if indicated.

10 HIV antibody titer, HBsAg determination, anti HCV, anti CMV antibody titer, HSV serology, and EBV panel. Patients who are known to be positive for CMV, HSV and/or EBV do not need to be retested.

	Screening/Baseline (prior to enrollment on treatment protocol)		On-Study/Course of Treatment (1 vaccine = 1 cycle)				Post-Treatment Follow-up		
	Within 3 Months	Within 4 Weeks	Within 7 Days	Day 0 ¹ (±5 d)	Day 14 (±5 d)	Day 28 (±5 d)	Day 42 (±5 d)	Day 56 (±5 d)	Subsequent Follow-up Visits ²
Assessments									
CBC w/differential			X	X	X	X	X	X	X
Chemistry panel ¹¹			X	X	X	X	X	X	X
PT/PTT			X	X					
Lymphocyte phenotyping (TBNK)				X			X	X	
Additional leukapheresis ¹²							X	X	
Correlatives¹³							X		
CPT tubes (8) (SB CPF)				X	X	X	X	X	X
SST tube (1) ([name] Lab)			X	X	X	X	X	X	X
Imaging									
CT, MRI, PET, and/or photography ¹⁴		X					X	X	X
Chest x-ray			X	X			X	X	X
Treatment/Intervention									
Peptide loaded dendritic cell vaccine ¹⁵				X	X	X	X		

11 Chemistry panel: Sodium (Na), Potassium (K), Chloride (Cl), Total CO₂ (bicarbonate), Creatinine, Glucose, Urea nitrogen (BUN), Albumin, Calcium total, Magnesium total (Mg), Inorganic Phosphorus, Alkaline Phosphatase, AST/GPT, ALT/GOT, Total Bilirubin, Direct Bilirubin, Total Protein, Total CK, Uric Acid

12 A 5 liter leukapheresis may be performed. If the patient is unable to undergo leukapheresis, approximately 96 ml of blood may be obtained. This will be conducted under 03-C-0277, and will only be performed at the first follow-up evaluation.

13 Research samples, as described in Section 5, prior to each vaccination and at each scheduled follow-up evaluation. Includes evaluation of specific lysis and cytokine release, metabolomic and bioenergetic studies (using Seahorse), intracellular FACS of cytokine production, ELISA-spot assays, and lymphocyte subset analysis may be used to evaluate the immunological correlates of treatment.

14 As performed at baseline to determine tumor response. If clinically indicated, other scans or x-rays may be performed, e.g., brain MRI, bone scan.

15 Administered subcutaneously and intravenously.

